7.2. Prohibited or Restricted Therapy

The following therapies are prohibited until study treatment has been permanently discontinued:

- Any investigational agent or investigational medical device.
- Therapeutic doses of oral anticoagulants (eg, warfarin or other coumarin-related agents, direct thrombin or direct FXa inhibitors, or antiplatelet agents such as clopidogrel, or chronic use of aspirin above low dose levels for cardioprotection per local applicable guidelines).
- Any nonprotocol systemic anticancer treatment (eg, chemotherapy, immunotherapy, radionuclides, drugs or herbal products used specifically for the treatment of the cancer under investigation).

- Concomitant use of denosumab with atezolizumab is prohibited due to a potential for increased risk of infections.
- Immunosuppressive agents including immunosuppressive doses of systemic corticosteroids with exceptions as stated in [Section 7.1](#).
- Metamizole (dipyrone) because of its potential for causing agranulocytosis.

The following therapies should be avoided until study treatment has been permanently discontinued or until otherwise specified:

- Local anticancer treatment including palliative radiation, ablation, embolization, or surgery with impact on tumor lesions should not be performed until radiographic progression per RECIST 1.1 has been established. If clinically unavoidable the investigator should consult the Sponsor prior to the procedure for safety guidance.
- Erythropoietic stimulating agents (eg, epoetin alfa and darbepoetin alfa) should not be used based on a report of increased risk of tumor recurrence/progression associated with erythropoietin (Wright et al 2007).
- Concomitant medications that are known to prolong the QTc interval should be avoided in subjects until they have permanently discontinued cabozantinib or sorafenib treatment (refer to <http://www.qtdrugs.org> for a list of drugs which have the potential to prolong the QTc interval).
- Live vaccines are prohibited while on study and until 5 months after last atezolizumab dose (eg, intranasal influenza, measles, mumps, rubella, oral polio, Bacillus Calmette-Guérin, yellow fever, varicella, and TY21a typhoid vaccines). The use of inactivated (killed) vaccines for the prevention of infectious disease requires Sponsor approval with the exception of an inactivated influenza vaccine, which can be given without Sponsor approval.

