- Bone scan, PET scan or plain films are not considered adequate imaging techniques to measure bone lesions.
- Lytic bone lesions or mixed lytic-blastic lesions, with identifiable soft tissue components, that can be evaluated by cross-sectional imaging techniques such as CT or MRI can be considered as measurable lesions if the *soft tissue component* meets the definition of measurability described above.
- Blastic bone lesions are non-measurable.

Lesions with prior local treatment

- Lesions situated in a previously irradiated area, or in an area subjected to other loco-regional therapy, are not considered measurable.

Imaging Methods

The same method of assessment and the same technique used to characterize each identified and reported lesions at baseline should be used during each follow-up assessment. All measurements should be taken and recorded in metric notation using a ruler or calipers. Imaging based evaluation is preferred to evaluation by clinical examination unless the lesion(s) being followed cannot be imaged but assessed by clinical examination (referring to biopsy-proven visible lesion(s) on the chest).

Chest x-ray: Chest x-ray will not be used for response assessment in this study.

Conventional CT and MRI: This guideline has defined measurability of lesions on CT scan based on the assumption that CT slice thickness is 5 mm or less. If CT scans have slice thickness greater than 5 mm, the minimum size for a measurable lesion is twice the slice thickness. MRI is also acceptable in certain situations (eg, for body scan) except for lung.

Use of MRI remains a complex issue. MRI has excellent contrast, spatial, and temporal resolution; however, there are many image acquisition variables involved in MRI, which greatly impact image quality, lesion conspicuity, and measurement. Furthermore, the availability of MRI is variable globally. As with CT, if an MRI is performed, the technical specifications of the scanning sequences used should be optimized for the evaluation of the type and site of disease. Furthermore, as with CT, the modality used at follow-up should be the same as was used at baseline and the lesions should be measured/assessed on the same pulse sequence. It is beyond the scope of the RECIST guidelines to prescribe specific MRI pulse sequence parameters for all scanners, body parts, and diseases. Ideally, the same type of scanner should be used and the

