6.9 Concomitant and Subsequent Surgeries/Procedures

Post-randomization radiation therapy and surgery/procedures that impacted the target lesion(s) (Yes, No, Unknown) will be summarized by treatment group for subjects in the PITT, ITT, P-Safety and Safety populations.

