7.1.1.2 Primary Estimand

The primary estimand for PFS is the difference in survival functions between treatment conditions in the duration of radiographic progression-free survival in the targeted population:

- irrespective of whether the assigned study treatment was given
- irrespective of clinical deterioration
- irrespective of whether local radiation was given to bone
- irrespective of surgical resection of non-target lesions
- in absence of any surgery to resect tumor lesions
- in absence of any other systemic or local non-protocol anti-cancer treatment
- in absence of any local radiation to soft tissue
- in absence of missing pre-randomization tumor assessment
- in absence of two or more missing consecutive adequate tumor assessments

Derived as follows:

Estimand attribute ¹	Primary definition		Rationale (as needed)
Population	Subjects randomized into the study intended to include patients with advanced HCC who have not received previous systemic anticancer therapy.		The initial clause “Subjects randomized into the study intended to include...” is included to align the estimand with the application of the ITT principle expected by regulatory reviewers
Endpoint	Duration of radiographic progression-free survival		
Intercurrent events	Event	Strategy	Rationale (as needed)
	Receipt of non-assigned study treatment or non-receipt of study treatment	Treatment policy	This strategy applied to align the estimand with the application of the ITT principle expected by regulatory reviewers.
	Clinical deterioration	Treatment policy	This strategy applied due to the nature of the primary endpoint, which is radiographic PFS.
	Receipt of local radiation to bone	Treatment policy	This strategy applied as local radiation to bone is typically palliative and does not directly confound radiographic evaluations of soft tissue.
	Surgical resection of non-target tumor lesions	Treatment policy	This strategy applied as target lesions are the primary focus of RECIST 1.1 evaluations.
	Surgical resection of target tumor lesions	Hypothetical	This strategy arises as a consequence of the convention of censoring for these intercurrent events that confound radiographic tumor assessments per RECIST 1.1., and the assumption in the Kaplan-Meier model that censored subjects would have behaved in a fashion similar to those not censored, i.e. not experienced these intercurrent event(s)
	Receipt of systemic non-protocol anti-cancer medications	Hypothetical	

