7.1.1.4 Primary Definition

For the primary analysis directed toward the primary estimand, duration of PFS is defined as the time from randomization to the earlier of either the date of radiographic progression per BIRC or the date of death due to any cause.

PFS (months) = (earliest date of progression, death, censoring – date of randomization + 1)/30.4375

General censoring rules for the primary analysis of PFS are described below, with details provided in Table 7Table 8 (analysis ID PFS-EP-1):

- Subjects who receive systemic or local NPACT or non-protocol radiation therapy (other than to bone) or surgery to resect target lesions before experiencing an event will be right censored at the date of the last tumor assessment prior to the date of initiation of subsequent therapy/surgery. If there is no such tumor assessment post randomization, the subject will be right censored on the date of randomization.
- Subjects who have not experienced an event (and are not otherwise censored) at the time of data cutoff will be right censored on the date of their last tumor assessment post randomization that is on or prior to the data cutoff date. If there is no such tumor assessment post randomization, the subject will be right censored on the date of randomization.
- Subjects who miss 2 or more scheduled tumor assessments followed by an event will be right censored on the date of their most-recent tumor assessment prior to the missing assessments. If there is no such tumor assessment post randomization, the subject will be right censored on the date of randomization.

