All sensitivity and supplemental analyses will include all subjects in the PITT population. Tabulated summaries of survival times, hazard ratios, and log rank test statistics as well as graphs of survival functions will be presented.

Table 8: Event and Censoring Rules for Primary and Sensitivity Analyses of Primary PFS Estimand

Estimand	Primary		Primary		Primary		Primary	
Analysis type	Primary		Sensitivity		Sensitivity		Sensitivity	
Analysis purpose	Primary		Evaluate assessment time bias		Evaluate assessor bias		Evaluate potentially informative censoring	
Analysis ID	PFS-EP-1		PFS-EP-2		PFS-EP-3		PFS-EP-4	
Analysis name	rPFS per BIRC		Uniform dates		rPFS per Investigator		rPFS per BIRC despite missing ATA	
Estimand endpoint	Radiographic PD		Radiographic PD		Radiographic PD		Radiographic PD	
Population	PITT		PITT		PITT		PITT	
Situation	Outcome	Date of Outcome	Outcome	Date of Outcome	Outcome	Date of Outcome	Outcome	Date of Outcome
Radiographic PD per RECIST 1.1 per BIRC	event	date of recorded PD	event	date of scheduled visit (or next scheduled visit if between visits)	NA	NA	event	date of recorded PD
Radiographic PD per RECIST 1.1 per Investigator	NA	NA	NA	NA	event	date of recorded PD	NA	NA
Death	event	date of death	event	date of death	event	date of death	event	date of death
Intercurrent events (excluding those with Treatment Policy strategy for all estimands)								
Clinical deterioration	NA	NA	NA	NA	NA	NA	NA	NA
Systemic NPACT (medications)	censored	date of last ATA* before first initiation of therapy	censored	date of last ATA* before first initiation of therapy	censored	date of last ATA* before first initiation of therapy	censored	date of last ATA* before first initiation of therapy
Local NPACT (medications)	censored	date of last ATA* before first initiation of therapy	censored	date of last ATA* before first initiation of therapy	censored	date of last ATA* before first initiation of therapy	censored	date of last ATA* before first initiation of therapy
Surgical resection of target tumor lesion(s)	censored	date of last ATA* before target lesion resection	censored	date of last ATA* before target lesion resection	censored	date of last ATA* before target lesion resection	censored	date of last ATA* before target lesion resection

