Local radiation: to soft tissue for disease under study	censored	date of last ATA* before non-target lesion resection	censored	date of last ATA* before non-target lesion resection	censored	date of last ATA* before non-target lesion resection	censored	date of last ATA* before non-target lesion resection
Missing data								
No baseline ATA	censored	date of rand.	censored	date of rand.	censored	date of rand.	censored	date of rand.
≥ 2 consecutive missing scheduled ATA immediately prior to analysis event	censored	date of last ATA* before missing visits	censored	date of last ATA* before missing visits	censored	date of last ATA* before missing visits	event	date of last ATA* before missing visits
Observation ongoing								
None of the above	censored	date of last ATA*	censored	date of last ATA*	censored	date of last ATA*	censored	date of last ATA*

ATA, adequate tumor assessment; BIRC, blinded independent review committee; ITT, intent-to-treat; NA, not applicable; PD, progressive disease; NPACT, non-protocol anti-cancer therapy (medications including radiopharmaceuticals but excluding local radiation)

Date of recorded PD = see SAP text.

* or date of randomization if no post-randomization ATA

Blue cells indicate changes from primary analysis.

Table 9: Event and Censoring Rules for Supplementary Analyses of Alternative PFS Estimands

Estimand	Alternative 1		Alternative 2		Alternative 2	
Analysis type	Supplementary		Supplementary		Supplementary	
Analysis purpose	Alternate progression definition		Alternate progression definition		Evaluate potentially informative censoring	
Analysis ID	PFS-EA1-1		PFS-EA2-1		PFS-EA2-2	
Analysis name	Investigator claims		rPFS or sNPACT		rPFS or sNPACT despite missing ATA	
Estimand endpoint	Radiographic or clinical PD		Radiographic PD or initiation of systemic NPACT		Radiographic PD or initiation of systemic NPACT	
Population	PITT		PITT		PITT	
Situation	Outcome	Date of Outcome	Outcome	Date of Outcome	Outcome	Date of Outcome
Radiographic PD per RECIST 1.1 per BIRC	NA	NA	event	date of recorded PD	event	date of recorded PD
Radiographic PD per RECIST 1.1 per Investigator	event	date of recorded PD	NA	NA	NA	NA
Death	event	date of death	event	date of death	event	date of death
Intercurrent events (excluding those with Treatment Policy strategy for all estimands)						
Clinical deterioration	event	date of determination of clinical deterioration	NA	NA	NA	NA

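### SAP Table 8 confines local anticancer therapy to medications, so thermal ablation and drug-free embolisation before BIRC progression escape the censoring that the primary PFS estimand calls for

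*SAP*

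**What the plan says.** **Estimand.** One bullet in SAP 7.1.1.2 sets primary PFS "in absence of any other systemic or local non-protocol anti-cancer treatment". The estimand table in the same section is narrower: its row for local therapy names medications only, under a hypothetical strategy.

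**Text rule.** SAP 7.1.1.4 censors at the last tumour assessment beforehand: "Subjects who receive systemic or local NPACT or non-protocol radiation therapy (other than to bone) or surgery to resect target lesions". It sends the reader to Table 8 for details.

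**Table 8.** There are four treatment-related censoring rows: systemic NPACT (medications), "Local NPACT (medications"), "Surgical resection of target tumor lesion(s"), and local radiation to soft tissue. The footnote defines the term: "NPACT, non-protocol anti-cancer therapy (medications including radiopharmaceuticals but excluding local radiation".

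**Protocol censoring rule.** Protocol 9.2.2.1 lists systemic NPACT, radiation other than to bone, and resection of target lesions. Local NPACT is absent.

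**Conduct.** Protocol 7.2 says: "Local anticancer treatment including palliative radiation, ablation, embolization, or surgery with impact on tumor lesions should not be performed until radiographic progression". Where treatment is clinically unavoidable, the investigator is to consult the sponsor first. Inclusion criterion 2 requires disease not amenable to curative approaches such as ablation, or to locoregional therapy.

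**Data.** SAP 6.9 deals with procedures separately from NPACT: "surgery/procedures that impacted the target lesion(s) (Yes, No, Unknown) will be summarized by treatment group". No censoring rule refers to it.

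**The concern.** The estimand, the text rule and the operational table give three different scopes for local therapy, and the protocol gives a fourth. The table is what will be programmed. If it is followed to the letter, PFS for a subject who has had a tumour ablated or embolised without drug continues to be observed as though nothing had intervened. The resulting estimate is not the one that SAP 7.1.1.2 describes.

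The comparison is alpha-controlled and the trial is open-label, so procedures need not be used equally in the arms. The same rows also define censoring for the secondary PFS test and for the response endpoints.

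**Working it through.** **1. Match each local treatment to a Table 8 row.**
- Chemoembolisation: contains a drug, so the local medication row applies.
- Radioembolisation: the footnote includes radiopharmaceuticals, so a row applies.
- Ethanol injection: arguably a medication.
- Resection of a target lesion: has its own row.
- External radiation to soft tissue: has its own row.
- RFA or MWA: not medication, resection or radiation, so no row applies.
- Drug-free embolisation: no row applies.

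The last two fall to the final row (none of the above), and observation continues.

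**2. Compare the scope of local therapy in each place.**
- SAP 7.1.1.2 bullet: any local treatment.
- SAP 7.1.1.4 text: local NPACT, not limited to medications.
- SAP 7.1.1.2 estimand table, Tables 8 and 9 and their footnotes: medications.
- Protocol 9.2.2.1: none.

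**3. Can such a procedure precede BIRC progression?** Yes, by two routes. One is the unavoidable case in Protocol 7.2. The other complies fully with the protocol: the investigator calls RECIST progression, after which 7.2 no longer discourages local treatment; study treatment and scans continue (Protocol 5.8.6.2, Table 4, and 5.8.6.3); and the BIRC has not yet called progression. Table 4 lists systemic NPACT, not local procedures, as a ground for ending imaging.

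**4. Trace the propagation.**
- Secondary PFS uses the primary methodology (SAP 7.4.1).
- Best overall response, and hence ORR, stops at the primary PFS censoring events (SAP 7.5.1).
- TTP and DOR take their dates from Table 8 columns (SAP 7.5.3 and 7.5.4).
- PFS-EP-2 to -4 have the same local rows.
- PFS-EP-11 to -14 start from PFS-EP-1 and reclassify only subjects already censored there. PFS-EP-3 and these four touch the investigator-progression route in part, but none isolates procedures.

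**5. Check the design figure.** Inputs from SAP 2.3: HR 0.6, two-sided alpha 0.01, power 90%, allocation 2:1.
- Events = (2.576 + 1.282)² / [(2/3)(1/3)(ln 0.6)²] = 257, as stated.
- Power at 257 events = 90.05%.
- Critical HR = exp(−2.576/√(257 × 2/9)) = 0.711, against 0.71 stated.

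The point does not turn on these numbers. For the cost of extra censoring, assume that 1% to 5% of the 372 PITT subjects are affected (the documents give no rate), that each loses one event, and that the analysis does not wait to replace them:
- 1% (3.7 subjects): power 89.6%.
- 3% (11.2): 88.5%.
- 5% (18.6): 87.3%.

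Because the analysis is triggered by events, the practical effect is a slightly later date rather than lost power.

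**The case against.** **The intention is already stated.** The estimand bullet and the 7.1.1.4 text both reach local therapy generally, and the SAP abbreviation list expands NPACT without limiting it to drugs. This stands as evidence that the narrow label was not a decision to keep ablated subjects under observation. It does not settle the matter, because 7.1.1.4 defers to Table 8, and the estimand table carries the same restriction.

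**Such procedures will be rare.** Criterion 2 and Protocol 7.2 both point that way. This stands, and it limits the importance of the point.

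**A reader might infer that treated lesions will be scored by the BIRC as stable or responding.** The documents do not show this. Reader methods are in the BIRC Charter, which is not included. Appendix E says "Lesions situated in a previously irradiated area, or in an area subjected to other loco-regional therapy, are not considered measurable", but under a heading on prior local treatment; it gives no rule for a target lesion treated after baseline.

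**A reader might infer a shift of about 5% in the hazard ratio.** The sum is 5% of 248 = 12.4 subjects; × 0.64 event probability = about 8 of about 159 expected combination-arm events, or 5% (0.71 × 0.95 = 0.675). At 1% the shift is about 1%. This is a ceiling on an assumed rate. It places every procedure in one arm, whereas equal rates would leave the ratio about unchanged. It also supposes that each procedure abolishes the event, although new lesions, non-target progression, other target lesions and death still count. The matching ORR figure, 12/248 = 4.8 points, needs every treated subject to become a confirmed responder.

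**A reader might infer that exempting bone radiation is the same defect.** It is not. The exemption is deliberate, agrees between protocol and SAP, and has a stated rationale. What remains is the uncommon bone lesion whose measurable soft-tissue component makes it a target.

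**Censoring may itself be informative.** True, and SAP 7.1.1.7 recognises this. It is the price of the hypothetical strategy that the SAP has already chosen for local therapy.

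**Conclusion.** The mismatch is real and should be corrected. Applied literally, Table 8 yields primary PFS, secondary PFS, ORR, TTP and DOR that differ from the stated estimand whenever thermal ablation or drug-free embolisation comes before BIRC progression.

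The effect is probably small. Its size and direction cannot be derived from the documents, which give neither a frequency by arm nor the BIRC's handling of lesions treated after baseline. The conclusion rests on the wording of the tables and on Protocol 7.2 contemplating these procedures, not on any assumed rate. It is a question of alignment and possible bias, not of power.

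**What to change.** 1. In the primary and alternative estimand tables (SAP 7.1.1.2 and 7.1.1.3), Tables 8 and 9 with their footnotes, SAP 7.1.1.4 and Protocol 9.2.2.1, define the category as: local NPACT (medications or tumour-directed procedures, including ablation and embolisation). Censor at the last adequate tumour assessment before the procedure. Resection and radiation keep their own rows.
2. Treat the widened category as composite in PFS-EA1-1 and hypothetical in PFS-EA2-1 and PFS-EA2-2, as the local medication row is now.
3. Identify cases from all recorded post-randomisation procedures, not only from the site-reported target-lesion flag. The BIRC selects its own targets, and the flag can be 'Unknown'.
4. Reword, rather than delete, the 7.1.1.2 bullet on surgery to resect tumour lesions so that it refers to target lesions. As written it conflicts with the bullet allowing non-target resection, but it is the only bullet that covers target resection.
5. In the soft-tissue radiation rows of Tables 8 and 9, the date cell refers to resection of a non-target lesion; it should refer to the radiation.
6. Optional: limit the bone-radiation exemption to bone lesions that are not targets.

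**Cost.** SAP and protocol wording and one derivation. The documents do not show whether procedure type is coded, so some review of individual records may be needed. A few more subjects would be censored, so 257 and 283 events may be reached slightly later.

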7.1.1.8 Exploratory Analyses

Exploratory analyses of the effect of baseline characteristics, stratification factors, and other variables on PFS may be conducted if necessary, using Cox regression models and subgroup analyses performed employing Kaplan-Meier methods. At the time of the primary analysis, PFS-EP-1 will also be repeated in the full ITT population.

The concordance in assessment of radiographic progression and the date between BIRC and investigator will also be summarized for the ITT population.

7.1.2 Duration of Overall Survival (OS)

7.1.2.1 Primary Estimand

The primary estimand for OS is difference in survival functions between treatment conditions in the duration of overall survival in the targeted patient population, irrespective of whether the assigned study treatment was given and irrespective of whether non-protocol anti-cancer therapy or radiation of any kind was given.

Derived as follows:

Estimand Attribute ¹	Primary Definition		Rationale (as needed)
Population	Subjects randomized into the study intended to include patients with advanced hepatocellular carcinoma who have not received previous systemic anticancer therapy.		The initial clause “Subjects randomized into the study intended to include...” is included to align the estimand with the application of the ITT principle expected by regulatory reviewers.
Endpoint	Duration of overall survival		
Intercurrent event(s)	Event	Strategy	Rationale (as needed)
	Receipt of non-assigned study treatment or non-receipt of study treatment	Treatment policy	This strategy applied to align the estimand with the application of the ITT principle expected by regulatory reviewers.
	Receipt of non-protocol anti-cancer therapy or radiation of any kind	Treatment policy	
Population summary	Lost to follow-up	Hypothetical	This strategy arises as a consequence of the convention of censoring at loss to follow-up and the assumption in the Kaplan-Meier model that censored subjects would have behaved in a fashion similar to those not censored, i.e. not experienced these intercurrent event(s)
	Difference in survival functions between treatment conditions		

¹See Appendix E for estimand terminology

